11.3 Analysis of Exploratory Objectives

11.3.1

Rib neurovascular bundles

We will evaluate the correlation between calculated doses to specific substructures in the chest wall and patient-reported pain, stratified by treatment group.

11.3.2

Urinary markers of bone turnover

We will conduct repeated measures analyses on urinary markers of bone turnover activity (one model per marker) and assess whether there is evidence of meaningful group by time interaction in the markers.

11.3.3

Urinary markers of pain-associated cytokines

Similar to above, we will conduct repeated measures analyses on urinary makers of pain-related biomarkers (cytokines and growth factors) where again we will be focused on examining evidence of group by time interaction.

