2.3 Exploratory Objectives

- 2.3.1 We will analyze novel anatomic dosimetric substructures on already completed radiation plans such as rib neurovascular bundles. These anatomical structures will be contoured onto the stored planning CT scans and the raystation planning system will allow us to calculate the dose that these structures received. We will assess the relation between this calculated dose and development of/grade of chest wall pain during follow-up. The standard structure that is routinely contoured for these cases is a crude ring encompassing 2-3 cm of the entire chest wall. We are hypothesizing that dose to specific substructures in the chest wall may be more useful in the prediction of chest wall pain development.
- 2.3.2 If funding permits, we will analyze, and compare between groups, the urine concentration of markers of bone turnover activity. These will all be assessed prior to SBRT and at the 6 month follow up visit post SBRT.
- 2.3.3 We will analyze and compare between groups the urine concentrations of pain-associated cytokines prior to SBRT and at the 6 month follow up visit post SBRT. Also, if funding permits, the urine concentration of pain-related neurotrophic growth factors (proNGF, proBDNF, GDNF), and neuropeptides (CGRP and Substance P) will be measured.

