5.3 Exploratory Outcomes

- 5.3.1 We will contour the neurovascular bundle that runs in the intercostal space for each patient within at least 3 cm of the planning tumor volume. We will then utilize stored treatment planning information and the raystation planning system to calculate the dose that this nerve bundle received at the time of treatment. As patients have already been assessed for development of chest wall pain at each follow up, we will assess for a dose response relationship between the dose to the nerve bundle and the subsequent development of and grade of any chest wall pain per the CTCAE v5.
- 5.3.2 Urine concentrations (pg/mL) of markers of bone turnover activity such as P1NP (procollagen type 1 pro-peptide), sclerostin, OPG (osteoprotegerin), TRAP5B, and pentosidine (an advanced glycation end-product (AGE)); will be analyzed using ELISAs. These markers will be assessed prior to SBRT and at the 6 month follow up visit post SBRT).
- 5.3.3 Urine concentrations (pg/mL) of pain-associated cytokines derived from the Isoplexis Codeplex Secretome Human Adaptive Immune and Innate Immune Chips which include GM-CSF, IL-1 β , IL-7, IL-17A, TNF- α , PDGF-BB, and VEGF will be assessed prior to SBRT and at the 6 month follow up visit post SBRT. In addition, other pro-inflammatory cytokines may be measured and analyzed on these chips as available. Also, if funding permits, the urine concentration (pg/mL) of pain-related neurotrophic growth factors (proNGF, proBDNF, GDNF) and neuropeptides (CGRP and Substance P) will be measured by ELISA.

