11.2 Analysis of Secondary Objectives

11.2.1

Percent change in cortical thickness across all time points

The percent change in mean cortical thicknesses from baseline will be assessed at 3 months, 6 months, 9 months, and 12 months post SBRT separately within regions of bone receiving 0 – 10 Gy, >10 – 20 Gy, > 30 – 40 Gy, and >40Gy. These outcomes will be compared using repeated measures analysis of variance (ANOVA).

11.2.2

Incidence and grade of chest wall pain

The incidence and grade of chest wall pain occurring inside the 50% isodose line will be collected and reported per modified CTCAE v5.0 (Appendix K) at 3 months, 6 months, 9 months, and 12 months post SBRT for all patients. Results will be compared between patients receiving placebo or risedronate. The incidence of G3 or greater chest wall pain will also be correlated with the volume of chest wall receiving at least 30 Gy or greater. The chest wall contour is defined as a 2 cm expansion from lung, from the costovertebral angle to the sternum.

11.2.3

Incidence of rib or vertebral fractures

The incidence of rib or vertebral fractures within the treatment field occurring at any time during the entire course of the study (12 months), will be reported and compared between patients receiving placebo or risedronate.

11.2.4

Urinary excretion of N-telopeptide (NTX)

The concentration of urinary NTX will be assessed at each time point from baseline to the conclusion of the study at 12 months. Results will be directly compared in each group.

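### The exploratory hypothesis that nerve-bundle dose may predict chest wall pain better than the standard chest wall ring is not tested by the planned analyses

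*Combined protocol and SAP*

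**What the plan says.** Section 2.3.1 commits to a relation: "We will assess the relation between this calculated dose and development of/grade of chest wall pain during follow-up". It then describes the comparator, "The standard structure that is routinely contoured for these cases is a crude ring encompassing 2-3 cm of the entire chest wall", and gives the reason for the work: "We are hypothesizing that dose to specific substructures in the chest wall may be more useful in the prediction of chest wall pain development".

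Section 5.3.1 defines the outcome as a dose response between bundle dose and "the subsequent development of and grade of any chest wall pain per the CTCAE v5". The analysis is one sentence in 11.3.1: "We will evaluate the correlation between calculated doses to specific substructures in the chest wall and patient-reported pain, stratified by treatment group".

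The conventional chest wall measure appears only in 11.2.2, under the secondary objectives: "The incidence of G3 or greater chest wall pain will also be correlated with the volume of chest wall receiving at least 30 Gy". The chest wall is contoured there as a 2 cm expansion from lung, and pain is graded on the modified CTCAE scale of Appendix K.

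**The concern.** The hypothesis is that one predictor may be better than another. The plan estimates each predictor's association with pain separately and never sets them against each other. Bundle dose and chest wall V30 come from the same treatment plan close to the same tumour, so they are likely to be correlated, although the documents give no value. If they are, a bundle correlation does not distinguish a better predictor from one that overlaps with the ring, and a positive result could be read as support for the new structure when the ring did as well.

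The pain outcome also shifts between sections, so even an informal comparison of the two reported correlations would not be like with like. If this is left open, the outcome and the bundle dose metric could be settled after the data are seen.

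**Working it through.** **Step 1: the sections side by side.**

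| Section | Dose measure | Pain outcome | Handling of arm |
|---|---|---|---|
| 2.3.1 | Bundle dose, with the 2-3 cm ring named as the standard | Development and grade of chest wall pain | Not stated |
| 5.3.1 | Bundle dose | Any chest wall pain and its grade, CTCAE v5 | Not stated |
| 11.3.1 | Substructure doses | Pain as reported by the patient | Stratified |
| 11.2.2 | Chest wall volume receiving at least 30 Gy | Grade 3 or higher, modified CTCAE | Not stated for this correlation |

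No section puts both dose measures on one outcome, in one model, or into a comparison of performance. The study calendar (6.6), the pain section (7.2) and the data table (10.0) name only the graded toxicity assessment and no patient-reported instrument. No section says whether bundle dose means mean, maximum or a volume measure.

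**Step 2: the plan's own figure.** The only sample-size figure is 42 per group for cortical thickness (11.4). With a difference of 0.22 - 0.11 = 0.11 mm, SD 0.20, one-sided alpha 0.05 and power 0.80, n = 2 × (0.20/0.11)² × (1.645 + 0.842)² = 40.9, or 41 per group. The t-test version gives 41.6, or 42. It reproduces, but says nothing about this analysis. It fixes the ceiling at 84 patients.

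**Step 3: can overlap alone produce a bundle correlation?** Assume only ring dose drives pain, with r = 0.40, and the two doses correlate at 0.70 to 0.85. The bundle then correlates with pain at 0.40 × 0.70 = 0.28 to 0.40 × 0.85 = 0.34 with no effect of its own. By Fisher z with n = 84 (√81 = 9), two-sided 0.05:
- r = 0.28: 0.288 × 9 - 1.96 = 0.63, power about 0.74
- r = 0.34: 0.354 × 9 - 1.96 = 1.23, power about 0.89

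**Step 4: what could a direct comparison show?** Assume 27% have grade 3 or higher pain (23 of 84) and dose correlations ρ of 0.5 to 0.85. For scale, 1.1 cites about 35% grade 3 or higher where more than 30 cc of chest wall receives 30 Gy. With AUCs near 0.5, Var(AUC) = (n + 1)/(12 n₁n₀) = 85/(12 × 23 × 61) = 0.00505. Take the correlation between the two AUCs as (6/π) arcsin(ρ/2). Then SE(difference) = √[2 × 0.00505 × (1 - that correlation)].
- ρ = 0.5: AUC correlation 0.483, SE 0.072, half-width 0.14
- ρ = 0.7: 0.683, SE 0.057, half-width 0.11
- ρ = 0.85: 0.838, SE 0.040, half-width 0.08

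A simulation with both AUCs near 0.64 to 0.69 gives the same half-widths to two decimals. At a 20% event rate the range is 0.09 to 0.16; at 35% it is 0.07 to 0.13. If 67 patients were evaluable (a 20% loss, assumed), the 27% case becomes 0.09 to 0.16. For 80% power the true AUC difference would need to be about 2.8 × SE, that is 2.8 × 0.040 = 0.11 to 2.8 × 0.072 = 0.20.

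Comparing correlations instead (ring 0.30, bundle 0.40 to 0.50, same range of ρ, n = 84), simulated power runs from about 16% to 97%. The answer depends heavily on values the documents do not give.

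**The case against.** The strongest reply is that the commitments in 2.3.1 and 5.3.1 are only to a dose-pain relation, which a correlation addresses. The comparative sentence is softly worded rationale in an exploratory objective, and no treatment comparison, sample size or safety rule depends on it. That stands and limits the weight of the point. It does not remove the mismatch, because the comparison is the stated reason for the new contours.

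The outcome conflict may also be partly wording. Section 5.3.1 says pain has already been assessed at follow-up, and the calendar schedules one chest wall assessment, on Appendix K. Any-grade and grade 3 or higher pain may simply be cut-points on one scale, and the 11.3.1 term may be loose language for the same grade. The contents of Appendix K are not in the supplied text, so this cannot be checked. It supports a simple alignment of wording and does not suggest that data are missing.

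The comparator is also not fully fixed: 2.3.1 describes a 2-3 cm ring with no dose metric, whereas 11.2.2 uses a 2 cm contour and V30. The latter is the natural stand-in, but the plan has to say so.

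A reader might infer that stratifying by arm halves the data (power for r = 0.30 is 0.49 with 42 patients against 0.80 with 84). The text does not support that. Stratified estimates can be combined across arms, and stratifying is reasonable if the drug could alter the dose-pain relation.

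**Conclusion.** The point holds as a gap between hypothesis and analysis: followed exactly, the plan does not test whether bundle dose is the better predictor, and its pain outcome differs between 5.3.1, 11.3.1 and 11.2.2. A reader might go further and conclude that the question cannot be answered in this trial. The documents do not support that, because chest wall V30, bundle dose and Appendix K grades are all planned for the same patients.

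Precision would be modest. The half-width of roughly 0.08 to 0.14 for the AUC difference rests on an assumed 27% event rate, assumed dose correlations of 0.5 to 0.85, and all 84 patients contributing. It will be wider with the withdrawals that 6.4 anticipates. Whether arms are pooled or stratified is a choice and not an error. The point is worth correcting because the change is cheap, but it bears on one exploratory objective only.

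**What to change.** - In 5.3.1 and 11.3.1, use the Appendix K modified-CTCAE grade that 11.2.2 already uses, and state the follow-up window.
- Name one bundle dose metric in advance.
- Keep the planned dose-pain correlation.
- Add to 11.3.1, for example: *In all patients with both dose measures, and accounting for treatment arm, chest wall V30 (contour of 11.2.2) and bundle dose will be compared as predictors of grade 3 or higher chest wall pain on Appendix K. The main measure is the paired difference in AUC with its 95% confidence interval. The added value of bundle dose over V30 in a joint model is supportive. The comparison is exploratory, and only large differences can be shown.*

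Naming the AUC difference as the main measure settles which result is read if the two disagree: the joint model addresses added value, which is not the same as being more useful. If the sponsor does not want the comparison, the alternative is to remove the comparative hypothesis from 2.3.1 and report only the dose-pain relation.

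The cost is analysis wording and a small amount of extra analysis. No new visits, scans or forms are needed.

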7.2 Incidence and Grade of Chest Wall Pain

Patients will be assessed at each routine follow up for development and or resolution of any chest wall pain/discomfort within the 50% isodose line. This will be graded per modified CTCAE v.5.

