10.0 Data Management

Data Collection Form	Data Storage Location
Informed consent document	EPIC
Protocol registration form	WISER/OnCore
All CT scans imaging and reports	EPIC/PACS
Adverse event log Appendix E	Oncore
Current Medications (Appendix G)	Oncore
Medication/Placebo administration form (Appendix H)	Oncore
Specific radiation related toxicities Modified CTCAE Chest wall pain Radiation pneumonitis Radiation Fibrosis (Appendix K and the pre-filled AE log)	OnCore
Radiation Treatment Details (Appendix N)	OnCore
Cortical Thickness Change (Appendix O)	OnCore
Urine bone turn over data (Appendix P)	OnCore
Fracture Incidence (Appendix Q)	OnCore
Adverse Events Log	WISER/OnCore
Biomarkers of Bone Turnover Activity	REDCap
Pain-Associated Cytokines	REDCap

Double Blind Design

We will work cooperatively with our IDS pharmacy supplying each patient either a single tablet of risedronate 150 mg or a single tablet of placebo. We will work directly with IDS pharmacy staff [contact], to procure identical placebo tablets as well as procedures for un-blinding and drug masking. As the hospital already has an unrelated protocol utilizing 150 mg risedronate vs placebo, many of these procedures are already in place. Patients will enroll through CDPM and be randomized through OnCore, but the investigator will not have knowledge of the randomization arm to which any patient has been assigned. The dispensing pharmacy will provide blinded samples and only the pharmacy will hold keys to un-blinding. At the conclusion of the study, when all patients have completed 12 months of follow up, the investigators will be unblinded to randomization of each patient.

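### Section 11.3.1 does not say whether the arms are combined in the nerve-bundle dose-pain analysis, and nothing masks the person contouring to pain grades

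*Combined protocol and SAP*

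**What the plan says.** Section 11.3.1 is a single sentence. It relates calculated dose in chest wall substructures to "patient-reported pain, stratified by treatment group". It names no coefficient, dose metric, pain time point, method of combining strata or interaction test.

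On the pain variable, Section 5.3.1 defines the outcome for the same aim as the "development of and grade of any chest wall pain per the CTCAE v5". Section 7.2 says of pain at routine visits: "This will be graded per modified CTCAE v.5". The form listed in the Section 10.0 table is "Modified CTCAE Chest wall pain", under Appendix K. Sections 5.2.2 and 11.2.2 also use the modified scale.

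On timing, Section 2.3.1 states: "We will analyze novel anatomic dosimetric substructures on already completed radiation plans such as rib neurovascular bundles". It adds: "These anatomical structures will be contoured onto the stored planning CT scans". Section 5.3.1 describes contouring and dose calculation and then continues: "As patients have already been assessed for development of chest wall pain at each follow up, we will assess for a dose response relationship".

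On masking, Section 10.0 keeps investigators blind to treatment arm until every patient has completed 12 months. No section mentions masking to pain.

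**The concern.** The question in this aim is whether dose to the nerve bundle predicts pain. It is not a question about the drug. An analysis reported arm by arm would answer it twice, each time on half the patients. The two answers could differ by chance, and a reader could take the difference for an effect of risedronate.

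The second issue is who can see what while contouring. The bundle is a small structure. Section 5.3.1 sets its extent only as a minimum distance of 3 cm around the planning volume, and no dose summary (maximum, mean or volume) is fixed. Someone who knows which patients had pain, and where, has some freedom in drawing the structure and choosing the summary. That freedom can create or strengthen the association being tested. Section 2.2.2 gives the subjectivity of chest wall pain as a reason for the placebo and double-blind design, but this aim has no matching safeguard.

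Third, three labels for one pain variable leave the analyst to choose the outcome.

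**Working it through.** **Inputs from the documents.** 84 patients in total (Section 3.3) and 42 per group (Section 11.4). Section 1.1 puts chest wall pain needing narcotics or analgesics at 30-40% in the department's patients.

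**The plan's own figure.** Section 11.4 sizes the trial for cortical thickness: difference 0.11 mm, SD 0.20, one-tailed 0.05, power 0.80. By the normal approximation, n = 2 × (1.645 + 0.842)² × (0.20/0.11)² = 40.9, so 41. The t-test version gives 41.6, so 42 per group with power 0.804. The 42 reproduces. The plan gives no power or precision for the nerve-bundle aim.

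**Assumptions for this aim.** Two-sided 5%, Fisher z, true correlation r = 0.30, all 84 evaluable. None of these is in the plan. Fisher z is only an approximate yardstick for an ordinal grade.

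**Information.** The variance of atanh(r) is 1/(n − 3), so the information is n − 3.

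- All patients, unstratified: 84 − 3 = 81.
- One arm alone: 42 − 3 = 39, which is 39/81 = 48%. The standard error rises by √(81/39) = 1.44.
- Estimated within arm and then combined: 39 + 39 = 78, which is 78/81 = 96%. The standard error rises by √(81/78) = 1.02.

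**Power and detectable correlation.** Power = Φ(atanh(r) × √information − 1.96), with atanh(0.30) = 0.3095. The smallest r detectable with 80% power is tanh((1.96 + 0.842)/√information).

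| Reading of the plan | Information | Power at r = 0.30 | Power at r = 0.35 | Detectable r |
|---|---|---|---|---|
| All 84, unstratified | 81 | 0.796 | 0.908 | 0.30 |
| Stratified, then combined | 78 | 0.780 | 0.898 | 0.31 |
| Each arm alone | 39 | 0.489 | 0.626 | 0.42 |

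If 10-30% of patients are not evaluable (assumed range), the detectable r becomes 0.32-0.36 unstratified, 0.32-0.37 combined and 0.44-0.50 per arm.

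**Chance disagreement.** If the true r is 0.30 in both arms and each is tested alone, the chance that exactly one is significant is 2 × 0.489 × 0.511 = 0.50.

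**Pain events.** If the 30-40% rate applies here (an assumption), 84 × 0.30 = 25 to 84 × 0.40 = 34 patients have pain, or about 13-17 per arm.

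**Pain labels side by side.** Section 11.3.1 says patient-reported pain; Section 5.3.1 says CTCAE v5; Sections 5.2.2, 7.2, 10.0 and 11.2.2 say modified CTCAE. The last two scales differ: Section 8.3 says the modified one takes account of whether pain is controlled with an NSAID or with a narcotic, gabapentin or nerve block. No patient-reported pain instrument appears in the study calendar, the data table or the list of appendices.

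**Timing and masking side by side.** Section 2.3.1 puts contouring on completed plans. Section 5.3.1 treats follow-up pain as already assessed. Section 10.0 masks arm only. Blinding to arm does not hide a pain grade. No arithmetic gives the direction or size of any resulting bias.

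**The case against.** A reader might infer that the plan runs a separate correlation in each arm and so throws away half its information. The text does not support that. Stratified can equally mean estimated within arm and then combined, and on that reading 96% of the information is kept. The figures of 0.49 and 0.42 apply only if each arm is reported alone. What stands is that the method is not stated and that the possible readings run from harmless to a halving.

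A reader might also infer that the trial relies on a pain measure it never collects. That is too strong. Grading chest wall pain depends on what patients say, and the calendar allows the 30-day grade to be taken by telephone. Patient-reported is plausibly loose wording for the collected grade. The text of Appendix K was not available for this check, so what it captures could not be confirmed. The mismatch is real but mostly editorial.

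On contouring, no section says that the person drawing the bundle knows the pain grades. The remark in Section 5.3.1 about pain already being assessed introduces the analysis rather than the contouring. The bundle is anatomically defined, and software computes dose from a fixed plan. These points limit the room for bias but do not remove it. Nothing requires contours to be finished before pain is known, or pain grades to be withheld.

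Finally, the aim is exploratory and no primary or secondary conclusion depends on it. That is correct, and it makes this a low-priority improvement.

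**Conclusion.** The point holds as a gap in specification and a missing safeguard. It is not a demonstrated loss of information or a demonstrated bias.

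- **Method.** Section 11.3.1 does not say whether the arms are combined. Reporting each arm alone would cut power from 0.80 to 0.49 at r = 0.30; combining strata would cost about two percentage points. Both figures rest on the assumed r, a two-sided 5% level, the Fisher z approximation and 84 evaluable patients.
- **Masking.** Contouring on stored plans after pain has been assessed, without masking to pain, allows bias in the dose-pain link. Its size cannot be computed from the documents.
- **Pain variable.** The three labels need aligning.

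The matter is minor in rank because the aim is exploratory, but it is cheap to settle. The masking rule helps only if it is adopted before the contours are drawn.

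**What to change.** 1. In Section 5.3.1, add that bundle contours and the dose metric are set and locked by existing staff without access to pain grades. The small cost is scheduling, so that the person contouring did not grade that patient's pain. The plan does not say who will contour, so the team should confirm that this can be arranged.
2. In Section 11.3.1, state one model in all patients, for example ordinal regression of the Appendix K grade on bundle dose, with arm as a covariate and dose-by-arm as a secondary term. Name the pain time point or summary; worst grade over follow-up is one option. Interpret the dose-by-arm term cautiously, given 13-17 patients with pain per arm at the assumed rate.
3. As an editorial alignment, name the modified CTCAE (Appendix K) grade as the pain variable in both Sections 5.3.1 and 11.3.1.

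The change is protocol and SAP wording plus one working rule. It needs no new patients, visits or data.

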7.4 Urine Biomarkers of Osteoclastic Activity and Bone Turnover

A single urine sample will be collected at baseline and at each follow up point (3,6,9,12 months). Samples will be collected in clinic and immediately transported to the laboratory of [name] on campus for storage in an minus 80 degrees C freezer designed for lab specimen storage. Urinary N-telopeptide (U-NTX) will be measured using ELISA based on an immobilized synthetic peptide with a specific sequence of amino acids matching a section of the N telopeptide (NTX) of type 1 collagen. Samples will be destroyed in biohazard waste immediately after analysis is complete.

The following detailed information on collection and analysis is provided from pacific biomarkers
<https://pacbio.com/ biomarker/assay-detail/148/>

Specimen Type: Urine (2nd morning void preferred; do not add preservative)

Optimum Volume: 1 mL

Stability:

2-8°C	-20°C	-70°C
1 week	3 months	1 year

Reporting units: nM BCE/mmol Cr (normalized)

Method: ELISA

Biological or Clinical Significance:

Bone resorption is a function of osteoclasts. These cells remove the mineral from bone and break down the organic matrix that is primarily comprised of type I collagen. Collagen is a cross-linked fibrous protein that forms the fabric of bone and most other connective tissues. Bone contains three polypeptide chains wound together in a helical structure. The ends of these chains (known as telopeptides) provide the intermolecular cross-linking that gives collagen its strength and resiliency. As these cross-linked domains from bone and other skeletal connective tissues are broken down, the pyridinoline cross-linking domains are released and ultimately excreted into the urine in the form of small peptides bound to pyridinoline (70%) and free pyridinoline (30%). One type of peptide-bound pyridinoline is the cross-linked N-telopeptide (NTX) which is unique to type I bone collagen. NTX can be used to identify fast losers of bone, to monitor therapy, to measure dose response, or to determine patient compliance with therapeutic prescription(s).

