11.4 Power and Sample Size

Per analysis of our retrospective human data and preclinical data, we estimate that the mean cortical thickness for both cases and controls pre SBRT will be approximately 1.35 mm. At 3 months, in the absence of any treatment, we estimate approximately 16.7% loss of cortical thickness to bones to 1.13 mm (thus resulting in a mean change of 0.22 mm in controls) within the treatment field in regions of bone receiving ≥ 30 Gy. Conservatively, if risedronate use limits loss of cortical thickness by at least half on a percentage scale (i.e., expected cortical thickness at 3 months in treatment group 8.4% lower, or 1.24 mm, corresponding to an expected mean change in treatment group of 0.11 mm), and assuming a standard deviation of delta cortical thickness in both treatment and control patients of 0.20,⁴ then with a power of 0.80 and a one-tailed alpha of 0.05, we anticipate that we will need 42 patients per group to achieve desired power to illustrate significantly higher preservation of cortical thickness at 3 months post SBRT.

There is no human data to accurately estimate how significantly risedronate will limit bone loss following SBRT, however in our pre-clinical rodent models, cortical thickness was preserved in all mice receiving risedronate and in two mice cortical thickness increased. We have no mechanistic reason to suspect that risedronate would cause increased bone loss and therefore are utilizing a one-tailed alpha in our calculations.

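### With two assayed time points, the planned group-by-time test for the exploratory urine markers is in its usual form a change-score comparison; adjusting for baseline is at least as precise and costs nothing

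*Combined protocol and SAP*

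**What the plan says.** For the bone-turnover markers, objective 2.3.2 states "These will all be assessed prior to SBRT and at the 6 month follow up visit post SBRT", and outcome 5.3.2 gives the same schedule: "These markers will be assessed prior to SBRT and at the 6 month follow up visit post SBRT". For the cytokines, objective 2.3.3 compares "urine concentrations of pain-associated cytokines prior to SBRT and at the 6 month follow up visit post SBRT". Section 7.4 describes a wider collection schedule, "A single urine sample will be collected at baseline and at each follow up point (3,6,9,12 months"), but sections 2.3 and 5.3 do not name the 3, 9 and 12 month samples for these assays.

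Section 11.3.2 plans one repeated measures model per marker, to "assess whether there is evidence of meaningful group by time interaction in the markers". Section 11.3.3 plans the same for the pain-related markers, "where again we will be focused on examining evidence of group by time interaction". Neither section mentions a baseline covariate, a common baseline mean, a covariance structure or a transformation. Section 11.4 sizes the trial for the CT primary endpoint only; no power is given for any urine marker.

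**The concern.** An interaction between arm and time is a natural target when a marker is followed over several visits. With one baseline and one follow-up value there is no trajectory to compare. If the model gives each arm its own baseline mean, the interaction reduces to the difference between arms in mean change from baseline.

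In a randomised, double-blind trial the arms share the same expected value in a sample taken before the tablet, so any baseline difference is chance. A change score subtracts the whole of that chance difference, whatever the correlation between the two samples. Baseline adjustment subtracts only the part that the correlation supports. Both estimate the same arm effect at 6 months; they can differ in precision.

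Precision matters here because the sample size was set for another endpoint, so the analysis method is the main lever left for these markers. Each time point is a single urine sample (section 7.4) and the follow-up window is plus or minus 8 weeks (section 6.6, footnote f), so a modest correlation is plausible. The documents give no value.

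**Working it through.** **The plan's own figure.** Section 11.4 assumes a difference of 0.22 − 0.11 = 0.11 mm and an SD of change of 0.20 mm, "with a power of 0.80 and a one-tailed alpha of 0.05". The normal approximation gives 41 per group. With the t distribution, power is 0.795 at 41 and 0.804 at 42, so the stated 42 per group is reproduced. It concerns cortical thickness; there is no corresponding figure for the urine markers to check.

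**Inputs for the markers.** Two assayed time points (sections 2.3, 5.3); 42 per group at full enrolment (section 11.4). Assumed, because the documents do not give them: the correlation rho between baseline and 6-month values, the SDs s0 (baseline) and s1 (6 months), and any effect size.

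**Step 1: is the interaction the change-score test?** One data set of 84 patients with complete pairs was simulated. The two-sample t-test on change, the repeated measures ANOVA interaction and the random-intercept mixed-model interaction all gave t = 1.4749 with SE 0.2112. Regression of the follow-up value on arm and baseline gave SE 0.1768 on the same data.

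**Step 2: variances per patient.**
- Change score: s0² + s1² − 2·rho·s0·s1.
- Baseline-adjusted: s1²·(1 − rho²).
- Difference: (s0 − rho·s1)². This is never negative, and is zero only when rho·s1 = s0.

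**Step 3: equal SDs (s0 = s1).** The ratio of change-score to adjusted variance is 2(1 − rho)/(1 − rho²) = 2/(1 + rho). SEs are in marker SD units with 42 pairs per arm, using √(2/42) = 0.218.

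| rho | SE, change score | SE, adjusted | Variance ratio | Power of change score where adjusted analysis has 80% (two-sided 5%) |
|---|---|---|---|---|
| 0.3 | 0.258 | 0.208 | 1.54 | 62% |
| 0.5 | 0.218 | 0.189 | 1.33 | 68% |
| 0.7 | 0.169 | 0.156 | 1.18 | 73% |
| 0.9 | 0.098 | 0.095 | 1.05 | 78% |

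At rho 0.5, 42 per arm analysed by change score carries the precision of 42 × 0.75 = 31.5 per arm analysed with adjustment. Simulation of 8,000 trials at each of rho 0.2, 0.5 and 0.8 gave adjusted-to-change variance ratios of 0.61, 0.74 and 0.90, against 0.60, 0.75 and 0.90 from the formula.

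**Step 4: unequal SDs (rho 0.5, s0 = 1).**
- s1 = 1.5: 1.75/1.6875 = 1.04.
- s1 = 2: 3/3 = 1.00, no gain.
- s1 = 0.7: 0.79/0.3675 = 2.15.

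So the size of the gain depends on two unknowns, rho and the SD ratio.

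**Step 5: an illustration of power.** For an assumed effect of 0.5 SD, equal SDs and 42 pairs per arm (two-sided 5%, with one degree of freedom charged for the covariate), power is 0.48 against 0.66 at rho 0.3, 0.62 against 0.74 at 0.5, and 0.83 against 0.89 at 0.7. If only 30 pairs per arm remained (also assumed), power at rho 0.5 would be 0.48 against 0.59.

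**The case against.** The strongest reply is that the plan says only that the analyses are repeated measures analyses. A model that constrains the arms to a common baseline mean is one of these, and its group-by-time term is the adjusted arm effect. If that is what the authors intend, nothing is lost and one clause settles it. This stands as far as it goes: the text is open, and the equivalence in Step 1 applies to the ordinary model with free baseline means and complete pairs. If 6-month samples are missing, a likelihood-based mixed model is not exactly the completers' change-score test either, though it still does not use the common baseline mean unless told to.

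It is also fair to say that the endpoints are exploratory, carry no alpha or decision rule, and that the bone-turnover assays, growth factors and neuropeptides depend on funding. That limits the consequence, not the correctness.

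A reader might infer more than the documents support in three ways:
- That adjustment gains precision whenever the correlation is below 1. Step 4 shows a case at rho 0.5 with no gain; the simple ratio needs equal SDs.
- That only two urine samples exist. Five are collected; two are named for these assays.
- That the powers in Step 5 describe this trial. They rest on an assumed effect and, for the main figures, on 42 pairs per arm. Fewer are likely at 6 months: eligibility asks for a life expectancy of only 3 months (3.1.4), and patients needing additional systemic chemotherapy for new or progressive disease are withdrawn from further follow-up (6.4).

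**Conclusion.** The point holds as a loss of precision, and it is minor. The planned interaction test is valid under randomisation: there is no bias and no inflation of type I error, and no main conclusion of the trial depends on it. In large samples the change-score form is never more precise than baseline adjustment, and it is less precise except where rho·s1 = s0.

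With equal SDs the variance penalty is 54%, 33% and 18% at rho 0.3, 0.5 and 0.7, and about 5% at 0.9. With unequal SDs it may be close to nothing or considerably larger. These figures assume complete pairs and free baseline means in the planned model. For the growth factors and neuropeptides, the sampling times are not restated in sections 2.3.3 and 5.3.3, so the point applies to them only if they follow the same two-sample schedule.

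**What to change.** In 11.3.2 and 11.3.3, state that the arm effect for each marker will be estimated in one of two ways, and report it with a confidence interval:
- by regressing the 6-month value on arm and baseline value; or
- by a repeated measures model that constrains the arms to a common baseline mean, in which the group-by-time term is the arm effect.

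Name the baseline sample. The study calendar (6.6) lists urine in the Baseline column, separate from Dosing, whereas 5.3.2 says only that it precedes SBRT, and the tablet is itself given before SBRT (6.1). The analysis text should say that the covariate is the Baseline-column sample, taken before the study tablet, so that adjustment cannot absorb an early drug effect.

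A log scale is optional; the precision argument does not need it, and it would require a rule for values below assay detection. The cost is a few lines of SAP wording, with no extra patient, sample or assay. Fixing the model before unblinding also removes any later choice between change-score and adjusted results across many markers.
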